4.6 Multicenter studies

This is a multicenter study however individual center's results will not be presented.

4.7 Multiple comparisons/multiplicity

As inferential statistical analyses will no longer be performed this section is not applicable.

4.8 Use of an efficacy subset of participants

Subset analyses will no longer be performed.

4.9 Active-control studies intended to show equivalence

Not applicable

4.10 Examination of subgroups

Subgroups will no longer be examined.

5 STUDY POPULATION CHARACTERISTICS

5.1 Subject disposition

The following outputs will be created.

Summaries:

- **Reasons for screen failures** (as collected on the Study Termination Screen Failure CRF page) will be summarized using the ES for overall for all screened study participants who failed to be randomized.

-
- **Disposition of study participants screened** will be summarized using the ES for overall, by region and by site. In this summary, the site number, principal investigator name, first subject in date, last subject out date, will be captured by randomized treatment, and by each analysis set (ES, RS, SS, PK-PPS).
 - **Disposition of Analysis Sets:** summary of disposition of study participants by treatments group, by analysis sets (ES, RS, SS, and PK-PPS) using the RS.
 - **Disposition and Discontinuation Reasons**, using the RS, will contain the number and percentage of study participants who:
 - Started study and started each study period (Dose Adaptation Period, Maintenance Period and SFU Period)
 - Completed the study and completed each study period study period (Dose Adaptation Period, Maintenance Period and SFU Period)
 - Discontinued study and discontinued in each study period (Dose Adaptation Period, Maintenance Period and SFU Period)
 - Primary Reason for discontinuation (premature study termination as collected in the Study Termination CRF)
 - **Discontinuation due to AEs**, using the RS to tabulate the total number of study participants who discontinued the study due to AEs by treatment group, and the categories: AE serious, fatal, AE non-fatal and other (AE non-serious, fatal).
 - **COVID-19 Disposition:** Disposition and discontinuation reasons using the RS will contain the number and percentage of study participants who started, completed and permanently discontinued Treatment Period / Observation Period overall and by pre-, and during the COVID-19 pandemic based on the start, completed and discontinuation date relative to the pandemic cut-off date. The pandemic start date is March 20, 2020. The discontinuation reason in each period will also be summarized. Discontinuation due to COVID-19 pandemic will be listed as sub-category under “Other” reason.

5.2 Protocol deviations

Important Protocol deviations will be summarized by treatment group, using the RS to include the number and percentage of participants with:

- a. No important protocol deviations
- b. At least one important protocol deviation and the
 - Inclusion criteria deviation
 - Exclusion criteria deviation
 - Withdrawal criteria deviation
 - Prohibited concomitant medication use
 - Incorrect treatment or dose
 - Treatment non-compliance

– Procedural non-compliance

- c. Number of Participants excluded from the PK-PPS (and all categories in item b above).
- d. A summary of number and percentage of participants with an important protocol deviation by relationship to COVID-19 and treatment group will be provided for the RS. Additionally, the summary will be repeated by pre- and during the COVID-19 pandemic based on the deviations start date relative to the pandemic cut-off date. The pandemic start date is March 20, 2020.

A by-study participant listing of important protocol deviations will be provided using the RS.

Note: The criteria for exclusion of study participants and/or study data from the PK-PPS will be defined in the Protocol Deviation Specification document.

6 DEMOGRAPHICS AND OTHER BASELINE CHARACTERISTICS

Unless otherwise specified, all summaries will be based on the RS.

6.1 Demographics

Demographic variables will be summarized on the RS, by categories mentioned below using descriptive statistics, by treatment group and overall.

Categories for continuous variables (including n, mean, SD, Median, Min and Max):

- Age (years) - at the time of study entry.
- Weight (kg)
- Height (cm)
- BMI (kg/m²) calculated as: $BMI = \frac{\text{Weight (kg)}}{(\text{Height (m)})^2}$

Categorical variables (using frequency counts and percentages):

- Age (18 - <65, 65 - <85, ≥85 years)
- Age (≤18, 19 - <65, ≥65 years)
- BMI (<25, 25 to <30, ≥30 kg/m²)
- Weight (<50kg, 50kg-<70 kg, 70-<100kg, ≥100kg)
- Gender (Male, Female)
- Race (American Indian or Alaska native, Asian, Black, Native Hawaiian or Other Pacific Islander, White, Other/Mixed)
- Ethnicity (Hispanic or Latino, Not Hispanic or Latino)
- Region (North America, Europe, Asia [excluding Japan], Japan)
- Country

By-study participant listings of demographics will be provided.

Childbearing potential will be listed for the RS.

6.2 Other Baseline characteristics

6.2.1 Baseline disease characteristics

Baseline disease variables will be summarized using the RS, using descriptive statistics by treatment group and overall:

- Age at first ITP diagnosis (years)
- Time since first confirmed diagnosis of ITP (as collected in the eCRF)
- Splenectomy (Yes/No)
- IgG level (g/L) for
 - Non-splenectomized participants
 - Splenectomized participants
- Platelet count ($\times 10^9/L$) (as collected in the eCRF)
- Degree of thrombocytopenia (platelet count $<$ or $\geq 15 \times 10^9/L$) (using data collected in the eCRF)
- ITP Duration (persistent or chronic primary ITP as defined in Section 2.3)
- Total number of prior unique ITP medications (continuous)
- Total number of prior ITP medications (continuous)
- Number of prior unique ITP medications (1, 2, and ≥ 3)
- Concomitant use of TPO-RAs (eg, Eltrombopag and/or Avatrombopag) (Yes/No)

Notes:

- Persistent or chronic primary ITP as defined in Section 2.3
- In addition, the number and percentages of study participants in each stratum for each stratification factor (splenectomy (yes/no), degree of thrombocytopenia (platelet count $<$ or $\geq 15 \times 10^9/L$)) will be presented.
- Data will be summarized using data captured or derived from eCRF.
- The duration of ITP for chronic ITP participants will be computed in years and it will be calculated as follows:

$\frac{\text{Date of Screening} - \text{Date of Diagnosis}}{365.25}$, where the date of diagnosis will be obtained from the ITP history eCRF page.

- The duration of ITP – for persistent ITP participants will be computed in months and it will be calculated as:

$\frac{\text{Date of Screening} - \text{Date of Diagnosis}}{30.5}$, where the date of diagnosis will be obtained from the ITP history eCRF page.

-
- Age at diagnosis (years) will be calculated as: $\frac{\text{Date of first diagnosis} - \text{Date of birth}}{365.25}$
 - If the date of diagnosis is missing, the duration of disease and age at first diagnosis will not be calculated. In the case of the day (of the date of first diagnosis) being missing, then the day will be imputed with the last of the month. In the case day and month being missing (for the date of first diagnosis), the date will be imputed with 31st December.
Note: if the imputation results in an imputed diagnosis date that is after screening date, then the diagnosis date will be imputed to the screening date.
 - The duration of ITP will be presented in the listings as follows:
 - In years to 1 decimal place for chronic primary ITP participants
 - In months (3-12) for persistent primary ITP participants
 - Unique Prior ITP is derived as follows:
 - To derive prior ITP medications, see Section 6.5
 - To derive unique: count all medications with [REDACTED] as one, count all medication with [REDACTED] as one, for remaining prior ITP medications count all unique standardized medication names (CMEFCOD)

6.2.2 Lifestyle

A listing for DILI CRFs (DILI patients only) data (alcohol use and illicit drug use in the past six months (yes/no)) will be created using the RS.

6.3 Previous and ongoing medical history

Previous and ongoing medical history will be summarized by treatment group and overall system organ class (SOC), high level group term (HGLT), high level term (HLT) and preferred term (PT). Medical procedures are not coded.

Previous and ongoing medical history will be listed (separated) for the RS by treatment group and will include the MedDRA SOC, high level group term (HGLT), high level term (HLT) and PT.

6.4 Procedure history and concomitant medical procedures

Procedure history and concomitant medical procedures will be listed using the RS.

6.5 Concomitant medications

Definitions:

Past Medications: defined as any medications that started and stopped before first administration of IMP.

This includes medications reported in the following eCRF pages:

- “ITP Treatment history”
- “Prior and Concomitant Medications”, if end date before first IMP date

-
- “Prior and Concomitant Medications ITP Treatment”, if end date before first IMP date.

Prior Medications: defined as any medications that started before the first administration of IMP.

This includes medications reported in the following eCRF pages:

- “ITP Treatment History”,
- “Prior and Concomitant Medications”, if start date before first IMP date.
- “Prior and Concomitant Medications ITP Treatment”, if start date before first IMP date.

Baseline Medications: defined as any medications that started prior to first administration of IMP and stopped after the first administration of IMP (classified as prior and concomitant medications). This includes medications reported in the following eCRF pages:

- “Prior and Concomitant Medications”, if start date before first IMP date and end date after first IMP date or ongoing
- “Prior and Concomitant Medications ITP Treatment”, if start date before first IMP date and end date after first IMP date or ongoing

Concomitant medications: defined as any medication that has been taken at least once after the first administration of IMP.

This includes medications reported in the following eCRF pages:

- “Prior and Concomitant Medications”, if end date after first IMP date or ongoing
- “Prior and Concomitant Medications ITP Treatment”, if end date after first IMP date or ongoing

Concomitant only medication: defined as any medication that started after first administration of IMP

This includes any medication reported in the following eCRF pages:

- “Prior and Concomitant Medications”, if start date after first IMP date
- “Prior and Concomitant Medications ITP Treatment”, if start date after first IMP date

Table 6-1 below summarizes concomitant medication classification with details around medication start and finish.

Table 6-1: Concomitant Medications Classification

Medication Started	Medication finished	Classification
Before 1st Dose IMP	Before 1st Dose IMP	Past Medications
Before 1st Dose IMP	Any time	Prior Medications
Before 1st Dose IMP	After 1st Dose IMP	Baseline Medications (= prior and concomitant)
Any time	After 1st Dose IMP	Concomitant
After 1st Dose IMP	After 1st Dose IMP	Concomitant Only Medications

All the categories mentioned above will be summarized separately for ITP medications; Non-ITP medications will be listed only (using the RS) to display the number and percentage of participants in each category by treatment group, overall and by Anatomical Therapeutic Chemical classification (ATC) class, presenting Anatomical Main Group (ATC Level 1), Pharmacological Subgroup (ATC level 3), and preferred term.

Any medications with missing dates will be handled as described in Section 4.2.2 in order to classify them as prior and/or concomitant.

Listings for ITP medications will be also produced using the RS.

Notes:

- WHODD Mar2021 will be used for ATC terms.

6.5.1 Assignment of medications to treatment period

- **Treatment Period:** The treatment period will include medications taken at least once between the first administration of IMP on Day 1, up to the earliest of:
 - Week 25 (for participants who roll over to TP0004)
 - [REDACTED] after the last dose of IMP
 - The early withdrawal visit.
- **Safety Follow-Up Period:** A medication will be assigned to the Safety Follow Up Period if it has been taken at least once from the day after the end of the Treatment Period up until the EOS visit.

6.6 Prohibited concomitant medications and rescue medication

6.6.1 Prohibited concomitant medication

All prohibited concomitant medication listed in section 6.4.2 in the protocol will be summarized on the RS using the number and percentage of study participants who received prohibited concomitant medication by ATC class, presenting ATC Level 1, ATC level 3, and PT, ordered

alphabetically for the ATC class and in terms of decreasing frequency for PT within ATC class by treatment group. In the event of ties, PT will be ordered alphabetically.

6.6.2 Rescue Therapy

All rescue therapies mentioned in section 6.4.3 in the protocol, identified if Rescue Medication is ticked as yes on CRF will be summarized using the RS.

The number and percentage of study participants who received rescue medication will be displayed by ATC class, presenting ATC Level 1, ATC level 3, and PT (ordered alphabetically for the ATC class and in terms of decreasing frequency for PT within ATC class by treatment group. In the event of ties, PT will be ordered alphabetically).

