6.4.3 Rescue therapy

Rescue treatment will be given as per standard of care and at the discretion of the investigator as described below. If such rescue therapy is given, the participant is allowed to continue IMP treatment (as per guidance below), and should continue to complete all remaining scheduled visits in the Treatment Period, as per the Schedule of Activities (Section 1.3). The following rescue therapies may be used:

- Any increase in concomitant ITP therapies above Baseline dose
- Any additional ITP medication/therapies including but not limited to:
 - Platelet transfusion (only in cases of severe bleeding)
 - Commercially available IVIg
 - Any systemically administered corticosteroids (above the background doses, ie, pulse, oral and iv steroids). Any systemic corticosteroids used for the management of infusion reactions or other medical conditions are also considered rescue therapy.
 - Immunosuppressants (except for those listed in Section 6.4.2).

Although the use of rescue therapy is allowable at any time during the study, the use of rescue therapy should be delayed, if possible, for at least 2 days following the administration of study treatment.

If IVIg, high dose corticosteroids, or platelet transfusion are given as rescue therapy, IMP treatment can commence at the same dose as previously when platelet counts are $<50 \times 10^9/L$. Dose can be up-titrated at a later timepoint, if needed, depending on platelet level.

A high dose of corticosteroids is defined as any iv administration of corticosteroids given for any reason or doubling of an oral dose resulting in a dose more than 20mg/day prednisone equivalent dose.

In case of an increase of Baseline oral corticosteroids, not resulting in doubling of the oral dose more than 20mg/day prednisone equivalent dose, an increase in the concomitant ITP therapies above Baseline, or in case of administration of immunosuppressants as rescue therapy, IMP administration can continue as per Schedule of Activities (Section 1.3) at a dose adjusted depending on the platelet level.

The date and time of rescue therapy administration as well as the name and dosage regimen of the rescue therapy must be recorded in the eCRF.

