4.4 Handling and definition of the Corticosteroid (CS) prednisone equivalent dose

For the purposes of further analysis and tabulations, all corticosteroid doses (including both prior and concomitant corticosteroids taken for any indication) will be converted to prednisone equivalent doses. The conversion table for systemic corticosteroids is presented in Table 4-2.

Systemic corticosteroids are those with a route of administration of oral, intravenous, or intramuscular. All others (including topical, ocular, nasal, subcutaneous, intraarticular, etc.) will be considered non-systemic steroids which will have a prednisone equivalent dose = 0mg/day.

Budenoside is considered non-systemic even if taken orally and will always be assigned a prednisone equivalent dose = 0mg/day.

The prednisone equivalent dose will be included in the listing.

For example, if the total daily dose of triamcinolone is 8mg, the equivalent total daily dose of prednisone will be 10mg. If a new corticosteroid is reported that is not in Table 4-2, the appropriate prednisone equivalent conversion will be determined and the prednisone equivalent dose will be included in a separate systemic corticosteroids concomitant medication listing.

If medications are available in [REDACTED] which are not in table below, then the dose equivalent to 5mg/day Prednisone will be provided by the physician for this new system CS and the TFL footnote will be updated with this information for the newly identified CS

Table 4-2: Prednisone equivalent doses of systemic corticosteroids/steroids

Corticosteroids /Steroids	Dose equivalent to 5mg/day Prednisone
Cortisone	25
Hydrocortisone	20
Deflazacort	6.5
Prednisone	5
Prednisolone	5
Methylprednisolone	4
Triamcinolone	4
Dexamethasone	0.75
Betamethasone	0.6

Notes:

- All non-systemic corticosteroids (including topical, ocular, nasal, subcutaneous, intra articular, etc.) will be assigned a prednisone equivalent dose = 0 mg/day.
- ATC2 Term = "C01AC06 CORTICOSTEROIDS FOR SYSTEMIC USE, [REDACTED]"

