8.1 Statistical analysis of the primary efficacy endpoint

8.1.1 Primary analysis of the primary efficacy endpoint

The primary efficacy endpoint will be analyzed according to the following estimands' attributes:

- (1) Treatment conditions: Placebo and rozanolixizumab (please refer to section 6 Study treatments in the protocol for details)
- (2) Population: Adult Study Participants with Persistent or Chronic Primary Immune Thrombocytopenia (ITP) who fulfill the inclusion / exclusion criteria according to the protocol.
- (3) Endpoint: Durable Clinically Meaningful Platelet Response of $\geq 50 \times 10^9/L$, for at least 8 out of 12 weeks during the last 12 weeks (Week 13 to Week 25)
This endpoint includes the platelet count recorded at Week 14 to Week 25 corresponding to the response achieved following dosing at Week 13 to Week 24)
- (4) Intercurrent Events: see below.

Table 8-1: Intercurrent Events (ICE), Intercurrent Events Strategies (ICES) and Missing data Strategies for the analysis of the primary endpoint

Intercurrent Events (ICE)	ICE Strategy	Missing data strategy
a) Use of Rescue therapy from Baseline prior Week 25	A composite strategy Participants impacted by any ICE (a, b, c and d) will be considered as non-responders after the time of event.	Not applicable Section 4.2.2
b) Participants who experience any TEAEs leading to permanent treatment discontinuation		
c) Participants who discontinue prior to receiving IMP		
d) Participants who do not have any post-treatment assessment		
e) COVID-19*	A composite strategy Participants impacted by ICE (e) will be considered as non-responders at the time of event.	

* COVID-19 Impact category: Temporary discontinuation of study drug, Permanent discontinuation of study drug, Termination of study participation and Relationship to COVID-19: confirmed, suspected, general or other as recorded in the COVID-19 impact eCRF form.

(5) Population-level summary: Owing to early termination of the study, the population-level summary will be provided using descriptive statistics.

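### The SAP's only rule for recognising rescue is a CRF tick, which can miss dose increases and non-ITP steroids that the protocol counts as rescue

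*SAP*

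**What the plan says.** **SAP 6.6.2** plans a summary of rescue therapy by ATC class. It points to the therapies in Protocol 6.4.3 and counts one when it is "identified if Rescue Medication is ticked as yes on CRF".

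**Protocol 6.4.3** lists what may be used as rescue:
- "Any increase in concomitant ITP therapies above Baseline dose"
- "Any additional ITP medication/therapies including but not limited to" platelet transfusion, IVIg, systemic corticosteroids above background, and certain immunosuppressants
- within the corticosteroid item: "Any systemic corticosteroids used for the management of infusion reactions or other medical conditions are also considered rescue therapy"

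The same section requires that the "name and dosage regimen of the rescue therapy must be recorded in the eCRF", along with date and time.

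**SAP Section 8** makes rescue consequential. Table 8-1 lists "Use of Rescue therapy from Baseline prior Week 25" as the first of five intercurrent events for the primary endpoint, and an affected participant is a non-responder from that point on. Neither that table nor those that follow say how rescue is identified.

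**SAP 4.4** says "all corticosteroid doses (including both prior and concomitant corticosteroids taken for any indication) will be converted to prednisone equivalent doses", but the stated use is limited: "The prednisone equivalent dose will be included in the listing". It is not linked to rescue.

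**The concern.** The protocol's definition turns mostly on drug and dose, which are recorded facts, while the SAP's only recognition rule is a site's yes/no entry. The two can disagree when a treatment qualifies under 6.4.3 but does not feel like rescue to the site.

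Two situations stand out. First, Protocol 6.4.1 permits background oral corticosteroids up to 20 mg/day prednisone equivalent, and eltrombopag, avatrombopag and fostamatinib at any dose, asking only that doses stay stable where possible. A site that raises one of these within the permitted range may see it as allowed background therapy. Second, a systemic steroid for an unrelated condition may be entered as ordinary concomitant medication.

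If such a course lifts the platelet count and no flag is set, later counts are credited to the randomized treatment. In time to first rescue, the participant is censored when an event should have been counted.

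**Working it through.** The plan gives no figure on this point to reproduce. The check is a comparison of passages, then a simple scaling.

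**1. Where the flag is used in the SAP**

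| Endpoint | SAP location | Role of rescue |
|---|---|---|
| Primary: durable response | Table 8-1 | Intercurrent event; non-responder afterwards |
| Cumulative weeks at or above 50×10⁹/L | Table 8-2 | Intercurrent event; response lost from then |
| Time to first response | Table 8-3 | Intercurrent event; later data leave the time at risk |
| Response by Day 8 | Table 8-4 | Intercurrent event; non-responder |
| Confirmed response (30×10⁹/L and doubling) | 8.2.4.1, following 8.2.3 | Intercurrent event |
| Time to first rescue | 8.2.5 | The event itself |
| ITP-PAQ Symptoms | 8.2.6 | No rescue rule in the SAP (Protocol Table 9-2 has one) |

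That is the primary endpoint and 5 of 6 secondary endpoints: four through an intercurrent event and one as the event.

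**2. Which unticked treatments have another safeguard**

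| Treatment | Rescue under 6.4.3? | Other safeguard |
|---|---|---|
| IVIg, or systemic steroid above the allowed background dose | Yes | Prohibited unless rescue (Protocol 6.4.2); prohibited use means discontinuation and withdrawal (6.4.2, 7.2); deviation category in SAP 5.2 |
| Steroid for a severe infusion reaction or anaphylaxis | Yes | Permanent discontinuation (Protocol 7.1.3, Appendix 24), so event (b) in Table 8-1 |
| Permitted ITP drug raised above Baseline, within its allowed range | Yes | None found |
| Permitted ITP drug newly added | Yes | Appears among concomitant-only ITP medications (SAP 6.5), with no link to rescue |
| Systemic steroid for a non-ITP condition, within 20 mg/day | Yes, as 6.4.3 is worded | None found in most cases |

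The last three rows are the gap. A non-ITP steroid above the permitted dose could also surface as prohibited medication.

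**3. What a missed flag does**

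- *Primary.* It changes the result only if the participant reaches 8 of 12 weeks, needs counts taken after the rescue to do so, and has no other intercurrent event.
- *Cumulative weeks, time to first response, Day 8.* Fewer counts are needed. SAP 8.2.1 accepts one qualifying count in a week, and a single qualifying count can set the first response.
- *Time to first rescue.* SAP 8.2.5 censors those without rescue at withdrawal or completion, so a missed event becomes a censored time.

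**4. Size per case**

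Inputs: 33 randomized (SAP 2.3) and 2:1 allocation. Assumed split: 33 × 2/3 = 22 and 33 × 1/3 = 11. Actual arm sizes are not stated.

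- One wrongly kept responder: 1/22 = 4.5 points on rozanolixizumab, 1/11 = 9.1 points on placebo.
- Three: 3/22 = 13.6 points, 3/11 = 27.3 points.
- Split off by one: at 21:12, 1/21 = 4.8 and 1/12 = 8.3 points; at 23:10, 1/23 = 4.3 and 1/10 = 10.0 points.
- At the planned 40:20: 1/40 = 2.5 and 1/20 = 5.0 points.

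The documents give no basis for the number of such cases, which may be zero.

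**The case against.** The other side has real force.

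- **The tick sentence belongs to a summary table.** It also refers to Protocol 6.4.3, so the tick can be read as the way that definition is captured. A reader might infer that the SAP states that its endpoints use the tick alone. It does not. That the tick drives Section 8 is an inference, resting on the absence of any other rule.
- **The most dramatic examples are mostly covered.** A reader might infer that an unticked immunoglobulin course, or steroids for an infusion reaction, would simply be credited as drug response. The documents do not support that in general. Steroids for severe reactions come with permanent discontinuation. IVIg and above-background steroids that are not rescue are prohibited, participants who take them leave treatment, and later missing counts are set to zero (SAP 4.2.1). What survives is a course handled as rescue but left unticked.
- **A review vehicle exists.** Important deviations are settled before unblinding (SAP 3.4). Completion guidelines and cleaning plans that are not available here may hold edit checks.
- **The definition is not fully closed.** The added-therapy list is open-ended and rescue is at the investigator's discretion, so not every case can be derived mechanically.
- **Little rides on it.** SAP 3.9 removes all formal efficacy testing.

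These points narrow the gap without closing it. The deviation review looks for prohibited medication. A permitted drug raised above Baseline is rescue but not a prohibited drug, and no SAP passage reconciles it with the tick.

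**Conclusion.** The point holds as a cheap improvement. The SAP should say how rescue is recognised in Section 8, because its only rule can miss treatments that Protocol 6.4.3 counts as rescue. The exposure lies mainly in within-range increases or additions of permitted ITP drugs and in systemic steroids for non-ITP conditions.

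The size rests on two unknowns: how many courses went unticked, and the arm sizes. Under the assumed 22:11 split, each wrongly kept responder is worth 4.5 or 9.1 points in a descriptive rate. No test or p-value is affected.

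A reader might also infer that rescue by itself decides the primary endpoint, or that the gap favours rozanolixizumab. Neither follows. Rescue is one of five intercurrent events in Table 8-1, and missed flags could occur in either arm.

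**What to change.** In SAP Section 8, define one rescue flag: the CRF tick is yes, **or** the medication records meet Protocol 6.4.3. The derived part would cover:
- an ITP drug started after first IMP (the concomitant-only class in SAP 6.5)
- an ITP drug at a dose above Baseline
- a systemic corticosteroid that qualifies under 6.4.3, using the routes and prednisone conversion in SAP 4.4

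State how the 6.4.3 corticosteroid item is read for non-ITP use at or below background, so that the derivation is unambiguous. List every case where tick and derivation disagree, and resolve these blind to treatment alongside the existing deviation review. Use the same flag for every rescue intercurrent event, for time to first rescue, and for the 6.6.2 table.

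The SAP already combines sources in this way elsewhere. It takes the worse of severity and intensity for adverse events (10.2.1), and joins an automatic flag with physician review for opportunistic infections (13.1).

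The cost is one derivation, one blinded listing, and case review for the open-ended added-therapy category. The responder count may fall.
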